**Patient Recruitment:**

Prior to enrollment, the clinical trial was approved by the respective institutional review boards at WRNMMC, Durham VAMC, and Duke University Medical Center and the trial was registered at ClinicalTrials.gov (NCT01928849). Patients scheduled for surgical amputation or revision were screened for trial participation at the three Medical Centers from 2013 to 2017.

Among those who were screened, a significant number had been added to the surgical schedules in a non-elective fashion at the Durham VAMC and Duke University Medical Center, and were not able to be approached for consent in a non-pressured environment given the short interim period between scheduling and surgery. Similarly,

patients scheduled for amputations following trauma were often excluded because of the urgency of surgery.

Inclusion/Exclusion:

Criteria for inclusion were individuals, age 18 years and older presenting for amputation, stump revision, or surgery for mangled limb (defined as limb injury with sensory or motor deficits consistent with injury to a major nerve).

Criteria for exclusion were severe traumatic brain injury, significant cognitive deficits or dementia of any cause, substantial hearing loss without alternative means of communication, spinal cord injury with permanent deficits, current pregnancy or lactation, end-stage liver disease or hepatic encephalopathy, current therapy with valproic acid or other valproates, coumadin, chlorpromazine, olanzapine, zidovudine, or monoamine oxide inhibitors (medications affected by valproic acid metabolism), diagnosis of seizure disorder requiring anti-epileptic medication, current therapy with tricyclic antidepressants doses greater than 50mg/day, current diagnosis of malaria requiring anti-malaria medication, or allergy to valproates or valproic acid.

Randomization:

After enrollment, randomization was performed within the respective investigational drug pharmacy according to the schedule provided by our statistician. Randomization was stratified by site and surgical intervention, ie, amputation, amputation revision, or surgery for mangled limb with equal probability of assignment to the valproic acid group

or the controlled placebo group. Patients, investigators, treating medical/surgical team, and study personnel were blinded to the assignment.

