#### Intervention / Treatment

The study medication (valproic acid oral solution 250 mg per 5 mL or placebo (similar tasting flavored syrup) was then administered in single-dispense units. The initial dose was given by the perioperative anesthesia team. Subsequent doses were stored on the hospital ward or in the ICU with the patient's other medications and administered by the

nurse every 8 hours, up to 7 days or until time of patient discharge from the hospital, whichever came first. Blinding was kept intact throughout the study for all patients.

Patients in both the placebo and intervention study arms received regional anesthesia (either peripheral nerve or epidural), with multimodal perioperative management according to the standard of care at each of the three institutions. Research blood samples were collected preoperatively, postoperatively (at the end of treatment with study drug or placebo), and at clinic follow-up (3 months or at time of adjudication). Valproic acid levels were measured at the completion of drug administration to confirm study compliance.

Clinical Assessment Tools:

Clinical assessments were performed at enrollment, daily during hospitalization, and at clinic follow-up (3 months). If a patient was not available at 3 months to collect adjudication data, the study outcome was determined at the 6-month research visit. Assessment tools for pain and function included the Numeric Rating Scale (NRS), a 0-10 integer scale of pain intensity where 0/10 represents no pain and 10/10 represents the worst imaginable pain, the Brief Pain inventory, short form(BPI) (1) and the Defense and Veterans Pain Rating Scale (DVPRS) (2). Phantom and/or residual limb pain was assessed using the Groningen Questionnaire Problems Leg Amputation (GQPLA) questions (3). Neuropathic pain was measured using the Self-Reported Leeds Assessment of Neuropathic Symptoms and Signs (S-LANSS) tool (4,5). The presence of complex regional pain syndrome was determined using the Budapest Clinical Criteria

(6). Opioid and medication use was evaluated preoperatively, during hospitalization, and at the final outcome determination.

Physical Exam:

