## **STATISTICAL ANALYSIS:**

Patient data were collected from patients at all study sites and entered into Research Electronic Data Capture (REDCap)TM. Data were analyzed using SAS version 9.4 (SAS Inc., Cary, NC).

Patient characteristics were summarized by treatment group using mean (SD) or median [Q1, Q3] for numeric variables and count (%) for categorical variables to assess randomization and ensure balance between treatment groups. We also compared the patient characteristics between those who did and did not return for follow-up to evaluate the possibility of response bias. Finally, plasma levels of valproic acid (VPA) were monitored to verify treatment adherence, and to determine the concentrations of VPA among treated patients.

The incidence of chronic pain, the primary endpoint, was reported by treatment arm and compared using a two-sample chi-square test and multivariable logistic regression adjusting for baseline pain severity, type of surgery (amputation, revision, other), and surgical indication (medical vs. trauma). We also investigated possible differences in treatment effect within patient sub-groups based on study site, surgery type, and reason for surgery.

Secondary endpoints and analysis of functional trajectory were planned including the change in BPI (pain and interference scores), DVPRS (pain and supplemental scores), opioid use, and neuropathic pain subtypes from baseline to time of adjudication

endpoint. Median [Q1, Q3] of the changes of mean scales from baseline was computed by arm and by assessed time between the two treatment groups via Wilcoxon rank sum test, and overall by the Wilcoxon signed rank test. Frequency and percentage of the categorical variables in above endpoints was reported overall, by treatment arm, and by assessed time. Total opioid consumption during the first and second postoperative day was summarized via median [Q1, Q3], and compared between groups via Wilcoxon rank sum test. Rates of mortalities, liver disorders, and infections was summarized by group and compared by Fisher exact or chi-square tests as appropriate to evaluate safety of valproic acid administration.

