Sample size was calculated for the primary endpoint based on the assumption that 65% of the non-treatment arm patients will experience significant chronic pain (NRS  $\geq 3/10$ , averaged over previous week). We believed these estimates to be conservative, based on this group's prior research cohort (7) and prior literature demonstrating a phantom pain incidence as high as 79% in amputees from various causes Ephraim, 2005. With a 12% drop-out rate at 3 months secondary to death and loss to follow up, and a type 1 error rate of 0.05, the planned study of 224 patients would have 83% power to detect a difference in the incidence of chronic pain of 20% (45% vs 65%) between two arms using a two-sided chi-square test. Due to difficulties in enrollment the study was stopped early after 107 patients completed the primary endpoint evaluation.

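### Day 1-2 opioid consumption is compared without adjustment for recorded preoperative opioid use or the randomisation strata: a valid test, but less precise than it need be

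*Combined protocol and SAP*

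**What the plan says.** The Statistical Analysis section gives the whole analysis of this endpoint in one sentence: "Total opioid consumption during the first and second postoperative day was summarized via median [Q1, Q3], and compared between groups via Wilcoxon rank sum". It names no covariate, stratification factor, effect estimate or confidence interval.

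Three other places bear on it:

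- **Clinical Assessment Tools (under Intervention / Treatment):** "Opioid and medication use was evaluated preoperatively, during hospitalization, and at the final outcome determination". A preoperative value therefore exists, but the text does not say whether it is a dose or a yes/no entry.
- **Randomization (under Patient Recruitment):** "Randomization was stratified by site and surgical intervention". Preoperative opioid use is not a stratification factor.
- **Primary endpoint (Statistical Analysis):** the plan does adjust here, by "multivariable logistic regression adjusting for baseline pain severity, type of surgery (amputation, revision, other), and surgical indication (medical vs. trauma"). Neither preoperative opioid use nor site is in that model, and the model is not extended to opioid consumption.

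Change in opioid use from baseline is a separate secondary endpoint. It uses the baseline value but runs to the time of adjudication, so it does not cover days 1 and 2.

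**The concern.** The trial mixes first amputations, stump revisions and mangled limbs. Preoperative opioid use plausibly varies across such patients and predicts what they need in the first two days, although the documents give no data on this. If it does, an unadjusted comparison leaves explainable variation in the error term. It also lets a chance excess of opioid-tolerant patients in one arm shift the result in either direction. Stopping early makes such an excess more likely.

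The strata raise a second issue. Perioperative care followed each institution's own standard, so consumption may differ by site. Balancing the arms on site and then ignoring site in the analysis overstates the standard error of the comparison.

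What is at stake is the usefulness of one of the few early outcomes that does not depend on the 3-month visit. The primary conclusion is not at stake.

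**Working it through.** **The plan's own figure.** No power, SD or effect size is given for opioid consumption. The only power figure, 83%, concerns chronic pain ("a difference in the incidence of chronic pain of 20% (45% vs 65%) between two arms using a two-sided chi-square test"). With 224 × 0.88 / 2 = 98.56 per arm, the usual pooled formula gives 81.1% and the unpooled one 82.1%. That is close to the stated value and has no bearing on this point.

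**Inputs from the documents.** Two arms with 1:1 allocation; 107 patients with the primary endpoint evaluated, used here as a proxy because the number with day 1-2 data is not stated.

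**Assumed inputs.** Effect 0.5 SD on the log scale; 40% opioid-naive before surgery; correlation ρ between preoperative and day 1-2 use of 0.3, 0.5 or 0.7; two-sided 5% level.

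**Step 1: variance removed.** Adjusting for a covariate with correlation ρ multiplies the variance of the treatment comparison by 1 − ρ², and the CI width by the square root of that.

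| ρ | 1 − ρ² | CI width factor | Equivalent unadjusted N (107 / (1 − ρ²)) |
|---|---|---|---|
| 0.3 | 0.91 | 0.95 | 118 |
| 0.5 | 0.75 | 0.87 | 143 |
| 0.7 | 0.51 | 0.71 | 210 |

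**Step 2: power.** As a check by hand, the rank sum test has asymptotic efficiency 3/π = 0.955 for normal data, so its standardised effect is about 0.5 × √(53.5/2) × √0.955 = 2.53. Power is about Φ(2.53 − 1.96) = 0.71. Simulation of the rank sum test against rank ANCOVA with preoperative use as the only covariate gives:

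| ρ | Rank sum | Rank ANCOVA, graded dose | Rank ANCOVA, yes/no only |
|---|---|---|---|
| 0.3 | about 70% | about 73% | 71-73% |
| 0.5 | about 70% | 79-80% | 77-79% |
| 0.7 | about 70% | 89-91% | 85-86% |

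The ranges span separate simulations. With no treatment effect, and over all simulated trials, both tests rejected in about 5%.

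**Step 3: chance imbalance.** The standardised baseline difference between two equal arms has SD √(4/N). At N = 107 this is 0.193, so the probability of a difference above 0.3 SD in either direction is 2 × (1 − Φ(0.3/0.193)) ≈ 12%. At the planned 224 the SD is 0.134 and the probability about 2.5%. In the simulated null trials with such an imbalance, the rank sum test rejected in about 7% (ρ = 0.3), 10% (0.5) and 20% (0.7). Rank ANCOVA stayed at about 4-5%. These are rates within the imbalanced trials only; they already form part of the overall 5%.

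**Step 4: site.** Take three equal sites, balanced randomisation within site, and a between-site spread of 0.5 residual SD (assumed). The rank sum test then has type I error of about 3% and power of about 63%. Adding site to the rank model restores about 5% and about 70%. At a spread of 0.3 the loss is small (power 67-68%); at 0.7 power falls to 53-56%. This loss does not depend on ρ.

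Steps 2 and 4 were run separately. A model with preoperative use, site and type of surgery together was not simulated here, so the gains should not be added.

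**The case against.** The strongest reply is that the plan contains no error. In a randomised comparison the rank sum test keeps its level, and that level already averages over chance imbalances. The endpoint is secondary and carries no power claim. This stands: the point is about efficiency and about results conditional on an imbalance. A reader might infer that the test is biased or its p-value invalid, but neither the documents nor the simulations support that.

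The size is also open to challenge, and these limits stand:

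- The correlation, the effect, the opioid-naive share and the site spread are all assumed. At ρ = 0.3 the gain is only about 3 points.
- Regional anaesthesia and multimodal care in both arms could weaken the correlation.
- Preoperative use may have been recorded only as yes/no, which reduces the gain to about 2 points at ρ = 0.3.
- The 107 are patients with the primary endpoint evaluated. If the planned 12% dropout applied, 107 / 0.88 ≈ 122 might have early data, and unadjusted power would be about 77%.

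Finally, the document is dated September 2018 and is written after the trial. It is tempting to say that an adjusted model should simply replace the rank sum test. The documents do not support that: it would put a choice made after the event in place of the stated analysis. Nor is adjustment free of drawbacks, because missing preoperative values need a rule.

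None of this removes the point. Preoperative use was evaluated, the strata are known, and no other part of the document adjusts this endpoint.

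**Conclusion.** The concern holds as an avoidable loss of precision in a secondary analysis. The stated test is valid. It leaves unused a preoperative value that the trial evaluated and ignores two factors on which randomisation was stratified.

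Under the assumptions listed, adjustment for preoperative use raises power from about 70% to between about 73% (ρ = 0.3) and about 90% (ρ = 0.7), or from about 70% to at most about 86% if preoperative use is yes/no only. Separately, ignoring site makes the test conservative to the extent that consumption differs by site.

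That the test is unadjusted is certain from the text; the size of the gain is not, and could be small. A non-significant result on this endpoint should be read with that in mind, and a significant one should be read beside the arms' preoperative opioid use. The primary conclusion is unaffected.

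**What to change.** Keep the stated rank sum result and the medians by arm. Beside them, report one adjusted analysis, labelled as supportive and post hoc:

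- **Model:** rank ANCOVA of total day 1-2 consumption on treatment, preoperative opioid use, site and type of surgery. Use the dose if it was recorded, otherwise yes/no, and say which.
- **Missing preoperative values:** a missing indicator, so that no patient is dropped.
- **Effect size:** a treatment difference in consumption with a 95% CI, for example a Hodges-Lehmann shift, because rank ANCOVA by itself gives a difference in ranks. In its usual form that shift is unadjusted and should be described so.
- **Description:** preoperative opioid use by arm, and the number of patients with day 1-2 data.

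Naming one model and one missing-data rule matters, since leaving alternatives open would add analyst freedom after the event. The cost is one sentence in the analysis section and a few lines of code, with no new data. The drawbacks are the handling of missing preoperative values and the post hoc status of the result. In a future protocol the adjusted analysis could be specified in advance as the main one for this endpoint.

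### Safety is tested by Fisher or chi-square with no risk difference, interval or upper bound; at the achieved size a non-significant result cannot support safety unless events are common

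*Combined protocol and SAP*

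**What the plan says.** The combined protocol and SAP deals with the safety analysis in one sentence, at the end of the secondary-endpoint paragraph under STATISTICAL ANALYSIS. It begins "Rates of mortalities, liver disorders, and infections was summarized by group" and goes on to say that these rates are "compared by Fisher exact or chi-square tests as appropriate to evaluate safety of valproic acid administration". It gives no effect measure, confidence interval, upper bound, acceptable excess or rule of interpretation for any of the three outcomes. It states neither a significance level nor sidedness for the safety tests, and it does not define the set of patients to be analysed for safety.

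The sample-size paragraph of the same section concerns chronic pain alone: "the planned study of 224 patients would have 83% power" for a 45% vs 65% comparison, with "a type 1 error rate of 0.05", "between two arms using a two-sided chi-square test". It then reports: "Due to difficulties in enrollment the study was stopped early after 107 patients completed the primary endpoint evaluation". No expected rate of death, liver disorder or infection appears anywhere.

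**The concern.** Both named tests take equal risk in the two arms as their null hypothesis. They can give evidence of harm. They cannot give evidence that harm is absent or small, because a large p-value arises equally from no excess and from too few patients. The sentence nevertheless gives the evaluation of safety as the purpose of the comparison, and it provides nothing else inferential from which to judge how large an excess the data rule out.

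What is at stake is the safety statement. A report that follows the sentence would give group rates and three p-values. If the p-values are non-significant, the reader learns nothing about whether an excess of 5, 10 or 15 percentage points remains compatible with the data. An interval answers that directly.

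**Working it through.** **Inputs from the document (STATISTICAL ANALYSIS; allocation from Randomization).** Planned N 224, equal allocation, 12% drop-out, type 1 error 0.05, two-sided chi-square, 65% vs 45%, stated power 83%; 107 patients evaluated for the primary endpoint.

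**Assumptions.** Two-sided 0.05 for the safety tests, since sidedness and level are stated only for the primary endpoint. Control-arm event rates from 2% to 25%, since none is given. Safety denominator: 107/0.88 = 121.6, about 122 patients or 61 per arm. This applies the planned drop-out to the achieved number; the number dosed is not stated. As a lower case I also take the 107 themselves, 53 control and 54 treated.

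**Step 1: the plan's own figure.** Evaluable per arm = 224 × 0.88 / 2 = 98.56. With pooled variance under the null:

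power = Φ{[0.20 − 1.96 √(2 × 0.55 × 0.45 / 98.56)] / √[(0.65 × 0.35 + 0.45 × 0.55) / 98.56]} = Φ{(0.200 − 0.139) / 0.0694} = 81.1%.

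The unpooled form gives Φ(2.881 − 1.960) = 82.1%. Both are within 2 points of the stated 83%, so the planning inputs are understood correctly. There is no corresponding figure for safety.

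**Step 2: chance of missing a doubling.** For control rate p and treated rate 2p, sum the product of the two binomial probabilities over every pair of counts for which the test does not reject. The test is uncorrected chi-square when all expected counts are at least 5 and Fisher exact otherwise, which is one reasonable reading of the plan's choice between the two.

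| Control vs treated | 53/54 per arm | 61 per arm | 112 per arm (as planned) |
|---|---|---|---|
| 2% vs 4% | 99% | 99% | 94% |
| 5% vs 10% | 91% | 86% | 70% |
| 10% vs 20% | 70% | 67% | 43% |
| 12% vs 24% | 64% | 59% | 34% |
| 15% vs 30% | 54% | 48% | 23% |
| 20% vs 40% | 37% | 32% | 9% |
| 25% vs 50% | 23% | 18% | 2.5% |

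At 61 per arm the miss rate is 51.5% at a control rate of 14% and 49.6% at 14.5%, so the crossing point is about 14%. With Fisher alone it is about 17%. At 53/54 the crossing point is about 16% (chi-square) to 18% (Fisher); at 112 per arm it is about 9% to 10%.

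**Step 3: one anchor in the document.** The sample-size paragraph reads "With a 12% drop-out rate at 3 months secondary to death and loss to follow up". Deaths are only part of that 12%, so on the plan's own assumption 3-month mortality is at most about 12%. Taking that ceiling as the control rate, a doubling is missed 59% of the time at 61 per arm, and more often at lower rates. The document has no similar anchor for liver disorders or infections.

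**Step 4: what an interval would add.** Newcombe 95% limits for d = p₁ − p₂, with (l, u) the Wilson limits of each rate:

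lower = d − √[(p₁ − l₁)² + (u₂ − p₂)²]; upper = d + √[(u₁ − p₁)² + (p₂ − l₂)²].

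- Hypothetical 6/61 vs 3/61: p₁ = 0.0984 (0.0459 to 0.1984), p₂ = 0.0492 (0.0169 to 0.1349), d = 0.0492. Lower = 0.0492 − √(0.0525² + 0.0857²) = −0.051; upper = 0.0492 + √(0.1001² + 0.0323²) = 0.154. Fisher p = 0.49, yet the interval runs from −5.1 to +15.4 points.
- Hypothetical 3/61 vs 3/61: d = 0, limits ±√(0.0857² + 0.0323²) = ±0.092. Fisher p = 1.0, yet an excess of up to 9.2 points is not excluded.

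**The case against.** The strongest reply is that the plan does not commit the error. A reader might infer that p > 0.05 will be taken as showing valproic acid to be safe. No sentence says so: there is no safety hypothesis, no margin and no rule for what follows from a non-significant test. That objection stands. What the document supports is narrower: the one inferential tool named for the evaluation of safety cannot yield a conclusion in favour of it.

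A reader might also infer that tests are the whole of the safety evaluation. They are not. Rates are also summarised by group, and anyone with the counts can compute an interval. The plan does not commit to doing so.

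The tempting general claim, that these tests would miss a doubling most of the time, is too strong as well. It depends on control rates that the document does not give. At 61 per arm it fails above about 14%, and at the planned 112 per arm above about 9% to 10%. Infection could be a common enough outcome to fall on that side.

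Finally, low power for harms is usual in a trial sized for efficacy, and sizing on the primary endpoint is no defect. The document is largely a past-tense account of a stopped trial, so what remains is a matter of analysis and reporting. All of this is fair. It limits the weight of the point but does not remove it, because adding the intervals needs only data already collected.

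**Conclusion.** The point holds in a limited form. The plan evaluates the safety of valproic acid with group rates and significance tests, and it specifies no measure of how large an excess harm the data exclude. A non-significant result therefore could not support safety for uncommon outcomes. At an assumed 61 per arm and two-sided 0.05, a doubling is missed more often than not up to a control rate of about 14%, and 67% to 99% of the time between 10% and 2%. For more common outcomes the tests do better, with under a third of doublings missed at 20% vs 40%.

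These sizes rest on an assumed denominator, assumed sidedness and level, and assumed event rates. The absence of any interval or bound rests on the text alone. The document states no safety conclusion, so nothing here shows that one was wrongly drawn. This is an inexpensive improvement to the analysis, and it leaves the primary result untouched.

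**What to change.** In the safety sentence under STATISTICAL ANALYSIS, replace the test-based evaluation with text to this effect: for mortality, liver disorders and infections, report by group the number and percentage with an event and the risk difference (valproic acid minus placebo) with a 95% Newcombe or exact confidence interval, among all patients who received study drug; interpret safety from the interval, including its upper limit; do not take a non-significant Fisher or chi-square p-value as evidence of safety. The p-values may stay as descriptive output. State the number of patients in the safety set, since 107 is the number evaluated for the primary endpoint and deaths count towards drop-out.

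The cost is SAP wording and a few lines of SAS on data already collected, with no new patients or procedures. The downside is that the safety statement becomes less favourable, because the upper limits will be wide.

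### Does the early stop at 107 evaluated patients call for restated power and a named confidence interval for the primary endpoint?

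*Combined protocol and SAP*

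**What the plan says.** The sample size paragraph of the STATISTICAL ANALYSIS section states the design in full. The control rate is "based on the assumption that 65% of the non-treatment arm patients will experience significant chronic pain". Attrition is given as "With a 12% drop-out rate at 3 months secondary to death and loss to follow up". The significance level is "a type 1 error rate of 0.05", and "the planned study of 224 patients would have 83% power to detect a difference in the incidence of chronic pain of 20" percentage points, "using a two-sided chi-square test". The paragraph ends with the disclosure: "Due to difficulties in enrollment the study was stopped early after 107 patients completed the primary endpoint evaluation".

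Earlier in the same section, the incidence of chronic pain "was reported by treatment arm and compared using a two-sample chi-square test and multivariable logistic regression adjusting for baseline pain severity", type of surgery and surgical indication. No risk difference, risk ratio or odds ratio is named, and the document mentions no confidence interval anywhere.

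**The concern.** The only power figure in the document belongs to a study that was not completed. A reader could carry the 83% over to the 107 patients actually evaluated, who are about 54% of the roughly 197 the plan expected to evaluate.

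The primary result could then be presented as two percentages and a p-value. At this size, a non-significant p-value does not by itself rule out the 20-point reduction the trial was built to find. Without an interval, an inconclusive result could be read as evidence that valproic acid does not work.

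**Working it through.** **Inputs.** All come from the sample size paragraph, except the 1:1 allocation, which is under Randomization.
- Control rate p1 = 0.65, treated rate p2 = 0.45, two-sided alpha 0.05 (z = 1.96).
- Planned N = 224, drop-out 12%.
- Achieved N = 107. These patients had already completed the endpoint evaluation, so the 12% is not deducted again.
- The split of the 107 by arm is not given; 53.5 per arm is assumed.

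**Formula** (pooled variance under the null, n per arm, p̄ = 0.55):

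power = Φ[(|p1 − p2| − 1.96·SE0) / SE1], with SE0 = √(2·p̄(1 − p̄)/n) and SE1 = √((p1(1 − p1) + p2(1 − p2))/n).

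**The plan's own figure.** 224 × 0.88 = 197.1 evaluable, or 98.56 per arm.
- SE0 = √(0.495/98.56) = 0.0709; SE1 = √(0.475/98.56) = 0.0694.
- (0.20 − 1.96 × 0.0709)/0.0694 = 0.88, so power = 81.1%.
- The unpooled version gives 82.1%. Exact enumeration of the uncorrected chi-square gives 80.4% at 98/99 and 82.1% at 99/99.

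The stated 83% is therefore within about 2 points and is not in dispute.

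**At 107 evaluated.**
- SE0 = √(0.495/53.5) = 0.0962; SE1 = √(0.475/53.5) = 0.0942.
- (0.20 − 1.96 × 0.0962)/0.0942 = 0.12, so power = 54.8%.

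| Variant at N = 107 | Power |
|---|---|
| Pooled, equal split | 54.8% |
| Unpooled, equal split | 56.5% |
| Exact, uncorrected chi-square (53/54 either way) | 55.5–56.2% |
| Pooled, split 64/43 either way | 53–54% |
| Continuity-corrected | about 47% |

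With control at 65%, 80% power needs a treated rate of about 38.2%, a difference of 26.8 points.

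**Precision.** The expected 95% half-width is 1.96 × SE1: 1.96 × 0.0942 = 18.5 points at 107, and 1.96 × 0.0694 = 13.6 points at 197.

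**Can the interval be obtained from what is specified?** Take a hypothetical result of 35/54 (64.8%) against 25/53 (47.2%).
- Difference = 17.6 points; chi-square p = 0.066.
- SE = √(0.648 × 0.352/54 + 0.472 × 0.528/53) = 0.0945.
- 95% interval: 17.6 ± 1.96 × 9.45 = −0.9 to 36.2 points.

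The calculation uses only the incidence and denominator in each arm. The specified logistic regression likewise estimates the treatment effect as an adjusted odds ratio with a standard error, and hence an interval.

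**How often the interval would be ambiguous.** If both true rates were 65%, exact enumeration shows the 95% interval still reaching the 20-point target in about 41% of trials at 107 (54/53), against 16% at 197 (98/99). So at 107, about 59% of such trials would still exclude the target.

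**The case for a change.** The strongest case for a change starts from the date. The document is dated September 2018, after recruitment and adjudication had ended in 2017, and it already reports the stop, so it is the natural place to state the consequence. The figure asked for is power at the pre-specified effect with the achieved N, so the usual criticism of power computed at the observed effect does not apply. Regression output is also not a reporting commitment: the same section spells out medians, quartiles and Wilcoxon tests for secondary endpoints, yet names no effect measure or interval for the primary one. The cost would be a few sentences.

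Much of this stands. The omissions are real, the arithmetic is right, and a report that gave only a p-value at this size would be poor. However, the case depends on what a later report might do. Nothing in the plan treats non-significance as absence of effect, and nothing in it stops the interval from being reported. Whether the trial's report gives one cannot be seen from this document.

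**Conclusion.** No change to the plan follows. The stop at 107 cut power for the 20-point target from about 81% (stated as 83%) to about 55%, and widened the expected interval from 13.6 to 18.5 points either side. Those figures assume a near-equal split, an uncorrected chi-square test and no covariate adjustment. A continuity correction would lower the power to about 47%, and the power of the adjusted regression cannot be derived from the document.

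No stated figure or rule is wrong. The planning power is attached to 224 patients and reproduces to within about 2 points. The shortfall and its reason are disclosed, with every input a reader needs to recompute the consequence. Once the data are in, the interval shows what the trial can and cannot exclude, and a restated power figure would change neither the estimate nor its interpretation.

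The unnamed effect measure is a gap that the specified analyses fill: the risk difference from incidence by arm, and the adjusted odds ratio from the logistic regression, each with its 95% interval. Giving both when the results are reported is ordinary practice and leaves endpoint, tests, population and data as they are.
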